### **5.7.2 Secondary efficacy variables**

#### **5.7.2.1. Average CSMS over the entire (truncated) GPS**

The average CSMS over the entire (truncated) GPS is calculated in the same way as the average CSMS over the peak GPS.

The primary efficacy analysis will be repeated for the average CSMS over the entire (truncated) GPS for the FAS.

Summary statistics will be provided for the average CSMS over the entire (truncated) GPS by treatment group.

### 5.7.2.2. Average CSMS-dSS and CSMS-dMS over the peak and the entire (truncated) GPS

The average CSMS-dSS over the peak and the entire (truncated) GPS and the average CSMS-dMS over the peak and the entire (truncated) GPS is calculated in the same way as the average CSMS over the peak GPS.

The primary efficacy analysis will be repeated for

- the averaged CSMS-dSS over the peak GPS for the FAS,
- the averaged CSMS-dMS over the peak GPS for the FAS,
- the averaged CSMS-dSS over the entire (truncated) GPS for the FAS, and
- the averaged CSMS-dMS over the entire (truncated) GPS for the FAS.

Summary statistics will be provided for all average scores by treatment group.

### 5.7.2.3. Average Total Combined Score (TCS) over the peak and entire (truncated) GPS

#### 5.7.2.3.1. Daily Total Combined Score (TCS)

The daily TCS is the sum of the dSS component of the TCS (TCS-dSS) and the dMS component of the TCS (TCS-dMS) calculated from the data recorded in the eDiary.

The TCS-dSS is calculated as the sum of the severity of conjunctival symptoms (2 items) and nasal symptoms (4 items).

**Table 3: Conjunctival and nasal symptoms of the TCS**

Conjunctival Symptoms	Gritty feeling/itchy/red eyes *
	Watery eyes
Nasal Symptoms	Blocked nose
	Runny nose
	Itchy nose
	Sneezing

\* Maximum of single items "Gritty feeling", "Itchy eyes" and "Red eyes" is used for analysis.

**Table 4: Relief medications and scoring of the daily medication score of the TCS**

Relief medication	Score
No relief medications used	0
Oral antihistamine	Each tablet taken corresponds to a score of 6 with a maximum daily score of 6
Ocular antihistamine	Each drop corresponds to a score of 1.5 per eye with a maximum daily score of 6
Intranasal corticosteroid	Each spray corresponds to a score of 2 with a maximum daily score of 8
Maximum daily Medication Score (dMS)	20

For scoring of the TCS-dMS, subjects who take oral corticosteroids will be allocated the maximum daily score of 20.

Hence, the TCS-dSS ranges from 0 to 18 and the TCS-dMS ranges from 0 to 20. The daily TCS thus ranges from 0 to 38.

No single symptoms or medications within a daily assessment were missing, i.e. no strategy was needed how to deal with this issue.

TCS, TCS-dSS and TCS-dMS will be listed by subject and day. Days within the peak GPS and the entire (truncated) GPS will be flagged accordingly.

#### **5.7.2.3.2. Average TCS, TCS-dSS and TCS-dMS over the peak and the entire (truncated) GPS**

The primary efficacy analysis will be repeated for

- the averaged TCS over the peak GPS for the FAS,
- the averaged TCS -dSS over the peak GPS for the FAS,
- the averaged TCS -dMS over the peak GPS for the FAS,
- the averaged TCS over the entire (truncated) GPS for the FAS,
- the averaged TCS -dSS over the entire (truncated) GPS for the FAS, and
- the averaged TCS -dMS over the entire (truncated) GPS for the FAS.

Summary statistics will be provided for all average scores by treatment group.

#### **5.7.2.4. Probability of well and severe days during the peak and entire (truncated) GPS**

Well and severe days are defined based on the CSMS.

A “**well day**” is defined as a day with:

- No use of relief medication on the particular day, i.e. CSMS-dMS = 0.
- A total daily symptom score  $\leq 2$  out of 18 (CSMS-dSS  $< 0.34$ ).

A “**severe day**” is defined as a day with a score of 3 in any of the 6 rhinitis/rhinoconjunctivitis symptoms used for CSMS-dSS calculation.

The probability of a well day or a severe day during the peak and the entire (truncated) GPS will be analysed using data on a by-day level per subject using generalised estimating equation (GEE).

#### **5.7.2.5. Total Symptom Score (TSS) following Conjunctival Provocation Test (CPT)**

##### **5.7.2.5.1. Conjunctival provocation test assessment**

Four symptoms (eye redness, tearing, itching and irritation) will be scored by the investigator in conjunction with the subject 10 minutes after application of negative control or allergen solution. The Total Symptom Score (TSS) at each time point will be calculated as the sum of the four individual eye symptom scores.

A frequency table will be created displaying the number of subjects who achieved a positive test result during the CPT and those who did not at each visit, i.e. Visit 1, Visit 1a, Visit 2, Visit 2a and Visit 12. This table will contain all subjects in the respective treatment group (FAS and PPS) and also contain the category “CPT not performed”. Percentages will be calculated based on the performed CPTs only.

##### **5.7.2.6. Immunologic parameters**

Immunological parameters analyses are

- total IgE [ku/L].,
- grass-specific IgE [ku/L].,
- grass-specific IgG4 [mg/L].,
- grass-specific IgE / total IgE, and
- grass-specific IgE / specific IgG4.

Summary statistics will be created per immunological parameter and visit (Baseline, Visit 12 and Visit 15 and the absolute change from baseline to Visit 12 and Visit 15) by treatment group. A 80% confidence interval will be included for the mean of the absolute changes from screening to the final visit.

The change from baseline in immunoglobulin measurements will be additionally analysed using the same linear mixed model as specified in the primary analysis with the baseline value as additional covariate. The corresponding least square (LS) mean differences (for all active treatment groups compared to placebo [separately and combined]) with 80% CIs will be presented.

The analysis will be performed for the change from baseline to Visit 12 and for the change from baseline to Visit 15.

#### 5.7.2.7. Rhinoconjunctivitis Quality of Life Questionnaire (RQLQ)

The RQLQ is a questionnaire which consists of 28 questions in 7 domains (activity limitation, sleep problems, nose symptoms, eye symptoms, non-nose/eye symptoms, practical problems, and emotional function). Each question is scored on a scale from 0 to 6 (0 = not impaired at all to 6 = severely impaired).

The standardised version of the RQLQ score (RQLQ (S) defined as the mean of all 28 responses) will be aggregated as an outcome variable on a subject level by taking the mean of the scores from Visits 13 and 14 that can be attributed to the entire (truncated) or peak GPS, respectively.

The RQLQ score will be calculated if at least one score at Visit 13 or 14 is reported during the entire (truncated) or peak GPS. It will be considered missing if the RQLQ questionnaire has not been filled at any of these visits. Missing values of the RQLQ score will not be imputed.

The total RQLQ score and its change from baseline (Visit 2) will be summarized by eCRF visit and treatment group for the FAS and the PPS. In addition, summary statistics will be created for the RQLQ during the entire (truncated) or peak GPS and its change from baseline.

The total RQLQ score during the entire (truncated) or peak GPS will also be analysed using similar models as defined for the primary efficacy based on observed cases only.

The linear mixed model will include the RQLQ score during the entire (truncated) or peak GPS as outcome variable, the treatment group as fixed effect and country as random factor. In addition, the baseline total RQLQ score will be included as further covariate.

The analysis will be performed for the FAS.

Missing values for the analysis of the primary efficacy endpoint or for the analysis of selected secondary efficacy endpoints will be imputed using multiple imputation. Missing values in average symptom scores will be imputed using multiple imputation on the subject. The imputation strategy allows the inclusion of all subjects from the FAS in the respective efficacy analysis.

## 5.8 Safety

Analysis of all safety and tolerability variables will be based on the safety population (i.e., all subjects who received at least 1 dose of IMP). Summary statistics will be provided for safety variables. Alert ranges will be defined for laboratory values lying outside the normal range to a clinically relevant degree. Any measurement fulfilling these criteria will be presented in subject listings.

### 5.8.1 Treatment exposure and compliance

The number and percentage of subjects having received treatment will be summarised per treatment group and treatment visit (treatment received from Visits 2/2a to 11) for the FAS (randomised treatment) and the Safety Set (actual treatment).

The actually received cumulative dose in SU is calculated based on the actually received kit and vial numbers entered in the eCRF. The planned cumulative dose is based on the randomised treatment.

Summary statistics will be provided for the cumulative dose in SU and the ratio of the cumulative dose actually received and planned for the FAS (randomised treatment) and the Safety Set (actual treatment).

### 5.8.2 Adverse events

All Adverse events during the course of the study will be coded using the medical dictionary of regulatory activities (MedDRA) current at the start of the study and summarised by treatment group. AEs will be summarised by treatment, primary system organ class (SOC), preferred term (PT), relationship assessment and severity.

All solicited AEs identified via separate phone calls for the US will also be entered in the general AE section of the eCRF. Therefore, no separate analysis will be conducted.

The SOCs as well as the PTs within each summary table will be sorted by frequency in the total column in decreasing order.

AEs will be reported separately as pre-treatment or screening period AEs (any AE occurring prior to the first injection of study medication) and treatment emergent AEs (any AEs after first injection of study medication).

In general, all adverse events will be listed by treatment group, subject number, and period. For AE onset and end dates, the study day relative to the first injection will be listed.

#### 5.8.2.1. Definitions related to adverse events

Pre-Treatment adverse event: Any AE with date and time of onset prior to the first injection of study medication. Pre-treatment AEs might also be termed Screening Period AEs.

Treatment emergent AE (TEAE): Any AE with date and time of onset after first injection of study medication. In case of (partially) missing date or time that could indicate a TEAE, it will be analysed as treatment emergent.

TEAEs during the treatment period: Any AE with date and time of onset after first injection of study medication and up to and including date of last injection of study medication + 28 days.

Adverse Drug Reactions (ADRs): Any AE that is possibly, probably or definitely related to study medication or the assessment of the relationship to study medication is missing as reported in the eCRF.

Adverse events related to study procedure: Any AE that was documented with causal relationship to a study procedure of “yes” in the eCRF.

Adverse events of special interest (AESI): Any AE that was documented as “AESI confirmed by Adjudication Committee” in the eCRF.

Local AE: Any AE that is documented with the category “Local (injection site) adverse event” in the eCRF.

Systemic AE: Any AE that is documented with the category “Systemic adverse event” in the eCRF.

Other AE: Any AE that is documented with the category “Other adverse event” in the eCRF, i.e. any adverse event that is neither local nor systemic.

AEs leading to premature discontinuation of treatment: Any AE for which action taken is documented as “Permanent discontinuation of the IMP” in the eCRF.

AEs leading to temporary discontinuation of treatment: Any AE for which action taken is documented as “Temporary discontinuation of the IMP” in the eCRF.

AEs leading to premature discontinuation of study: for which action taken is documented as “Withdrawal from the Study” in the eCRF.

Duration of adverse event (expressed in [days]) is calculated as follows:

- End date/time of AE – onset date/time of AE
- In case of missing onset time or missing end time: end date of AE – onset date of AE + 1
- In case of (partially) missing onset date or (partially) missing end date no calculation will be done
- In case of ongoing end date/time (outcome = recovering, not recovered or unknown), date of study termination will be used as documented at the end of the study page or the early termination page of the eCRF.

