Abbreviations: AE = adverse events; AESI = adverse events of special interest; CPT = conjunctival provocation test; CSMS = combined symptom and medication score; dMS = daily medication score; dSS = daily symptom score; GPS = grass pollen season; Ig = immunoglobulin; PEFr = peak expiratory flow rate; RQLQ(S) = rhinoconjunctivitis quality of life questionnaire with standardised activities; SU = standardised units; TCS = total combined score; TSS = total symptom score.	

Overall design:

This will be a multi-centre, randomised, parallel group, double-blind, placebo-controlled exploratory study to explore the efficacy and safety of PQ Grass. Subjects will be assigned in a ratio of 2:2:1:1 (PQ Grass conventional posology, PQ Grass extended posology, placebo containing MCT and placebo without MCT, respectively) to receive one of the following treatment options prior to the onset of the grass pollen season (GPS):

- **PQ Grass conventional posology:** 4 injections of placebo without MCT followed by 6 injections of PQ Grass (900, 2700, 6000, 6000, 6000 and 6000 SU sequentially), to achieve a cumulative dose of 27600 SU *or*
- **PQ Grass extended posology:** 4 injections initially of PQ Grass (900, 2700, 6000, 6000 SU sequentially) followed by 1 injection of placebo without MCT, followed by 1 injection of PQ Grass (6000 SU), followed by 3 injections of placebo without MCT and thereafter 1 injection of PQ Grass (6000 SU) to achieve a cumulative dose of 27600 SU *or*
- **Placebo containing MCT:** 4 injections of placebo without MCT followed by 6 injections of placebo containing MCT *or*
- **Placebo without MCT:** 10 injections of placebo without MCT.

The study includes 4 periods, encompassing 15 visits to the study site and at least 2 follow-up telephone calls. Subjects will be provided with enough relief medication to cover them through this period by the study site. Eligible subjects will be randomised to either PQ Grass (conventional posology), PQ Grass (extended posology), placebo containing MCT or placebo without MCT treatment groups and will receive the first injection at the study. Subjects will thereafter return to the study site at subsequent visits during the treatment period (Visit 3 to Visit 11) to receive the remaining injections. The average duration of the treatment period will be approximately 16 weeks.

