During the GPS, subjects will record their allergic rhinitis/rhinoconjunctivitis symptoms and use of relief medications in an electronic diary (eDiary). The primary symptom and medication scores during the peak GPS and the entire (or truncated) GPS calculated according to the European Academy of Allergy and Clinical Immunology (EAACI) recommendations for the CSMS (primary endpoint) will be compared between the active and placebo treatment groups.

Subjects will return to study site for a follow-up visit approximately 2 weeks after Visit 12 (Visit 13) and 5 weeks after Visit 13 (Visit 14). At Visit 15 (approximately 5 weeks after Visit 14), subjects will return their eDiaries and relief medications, and post-treatment assessments for safety and efficacy parameters will be carried out.

A safety follow-up will be conducted by telephone at 3 and 6 months following the last injection.

Target population: Adult (18 to 65 years inclusive) subjects with seasonal allergic rhinitis and/or rhinoconjunctivitis due to grass pollen exposure (with or without allergic asthma that is well controlled).

Study treatments, dosage and mode of treatment:

Active Treatment:

Each PQ Grass injection will consist of extracts of grass pollen, which are chemically modified by treatment with glutaraldehyde and adsorbed to L-tyrosine.

The injections will be supplied at concentrations of 900, 2700, and 6000 SU per 1.0 milliliter (mL) and 50 microgram (μg)/1.0 mL of MPL adjuvant, 2% weight per volume (w/v) L-tyrosine and 0.5% (w/v) phenol.

Reference Therapy:

2 forms of placebo will be used; placebo containing MCT (L-tyrosine 2% [w/v] and phenol 0.5% [w/v]) and placebo without MCT (Buffered saline with 0.5% phenol [w/v]).

Dose/Dose schedule:

PQ Grass or placebo will be administered during Visits 2 to 11. Visits 2 to 4 will be approximately 1 week apart, Visit 4 to 5 will be approximately 4 weeks apart, Visit 5 to 6 will be approximately 3 weeks apart and Visits 6 to 11 will be approximately 1 week apart.

Statistical methods

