**Table 1 Populations for analyses**

Population	Description
Full Analysis Set (FAS)	All subjects who received at least 1 injection of the IMP. The analysis will follow the intention-to-treat principle and will analyse subjects according to the treatment group to which they were randomised.
Safety Set (SAF)	All subjects who received at least 1 injection of the IMP. Subjects will be analysed according to the treatment that they actually received.
Per Protocol Set (PPS)	A subset of the FAS and will exclude all subjects with major protocol deviations, and all subject with an in-sufficient level of in-season assessments during the peak GPS.

The SAF will be used for all evaluations of safety and tolerability. No participant of the BDRM had knowledge of treatment assignments of individual subjects.

The FAS and the PPS will be used for the evaluation of efficacy; the FAS will be the primary analysis set, and the PPS will be used for sensitivity analyses. The criteria used for inclusion of each subject into the respective analysis sets are detailed in the BDRM plan and the final decisions are documented in the BDRM minutes.

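### TEAE tables count about 9 weeks of placebo injections under conventional PQ Grass; a supplementary split at Visit 6 would undo the dilution and add a 50-versus-100 randomised comparison

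*SAP*

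**What the plan says.** SAP 5.8.2.1 defines the event class on which the safety tables rest: "Treatment emergent AE (TEAE): Any AE with date and time of onset after first injection of study medication". The definition has no end date and does not depend on which product was injected. A second, bounded category (TEAEs during the treatment period) runs "up to and including date of last injection of study medication + 28 days".

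The Protocol (Overall design) gives four ten-injection sequences, at Visits 2 to 11:

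- Conventional: "4 injections of placebo without MCT followed by 6 injections of PQ Grass".
- Extended: "4 injections initially of PQ Grass (900, 2700, 6000, 6000 SU sequentially) followed by 1 injection of placebo without MCT", then PQ Grass at two of the remaining five injections and placebo without MCT at the other three.
- MCT placebo: "4 injections of placebo without MCT followed by 6 injections of placebo containing MCT".
- Placebo without MCT: "10 injections of placebo without MCT".

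On spacing, the Protocol (Dose/Dose schedule) puts Visits 2 to 4 about a week apart and continues: "Visit 4 to 5 will be approximately 4 weeks apart, Visit 5 to 6 will be approximately 3 weeks apart". Visits 6 to 11 are again about weekly.

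SAP 5.8.2.2 tabulates TEAEs, ADRs, SAEs, AESIs, local and systemic AEs and discontinuations by treatment group, SOC and PT. SAP 5.1.1 adds a pooled PQ Grass column by default and separates tables by period where appropriate, but none of the periods it names begins or ends at Visit 6. SAP 5.8.2.3 adds a table of AEs, ADRs and severe AEs after each injection.

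**The concern.** A reaction to buffered saline at Visit 3 in a conventional-arm subject is reported in a PQ Grass column some weeks before that subject receives any PQ Grass. The pooled PQ Grass column combines one arm exposed from week 0 with another exposed from about week 9. Because an incidence table counts each subject once per class, a lead-in event can hide a later event of the same class, and a real excess after Visit 6 is shrunk.

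There is also a missed opportunity. Until Visit 6 only the extended arm receives PQ Grass; the other three arms all receive the same placebo. That is a clean randomised contrast, and no planned table pools those three arms. Safety and tolerability are a stated secondary objective, and the trial examines two posologies, so when events occur relative to first exposure matters to the reader.

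**Working it through.** **Arm sizes.** 150 subjects at 2:2:1:1 give 150 × 2/6 = 50, 50, and 150 × 1/6 = 25, 25. This reproduces the figures in the Protocol's Statistical methods.

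**Calendar (Protocol, Dose/Dose schedule).** Weeks from the first injection: Visit 2 = 0, Visit 3 = 1, Visit 4 = 2, Visit 5 = 6, Visit 6 = 9, Visit 11 = 14. The lead-in is 1 + 1 + 4 + 3 = 9 weeks. As a share:

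- of the injection schedule, 9/14 = 64%;
- of the bounded treatment-period window (14 + 4 weeks), 9/18 = 50%;
- of the time to the 6-month call (14 + 26 weeks), 9/40 = 22.5%.

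The Protocol's Overall design gives the treatment period as about 16 weeks, while the visit gaps sum to 14; the two passages should be reconciled. With 16 weeks the second share is 9/20 = 45%.

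**Dilution.** The documents give no AE rates, so this is an illustration. Assume a constant weekly background hazard h, doubled by PQ Grass from Visit 6, over the 18-week window (9 weeks before Visit 6 and 9 after).

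- Subjects of 50 with a first event in the lead-in = 50 × (1 − exp(−9h)).
- Risk ratio over 18 weeks = (1 − exp(−27h)) / (1 − exp(−18h)).
- Risk ratio from Visit 6 = (1 − exp(−18h)) / (1 − exp(−9h)).

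| h per week | Lead-in first events, of 50 | Risk ratio, 18 weeks | Risk ratio, from Visit 6 | Risk difference, 18 weeks | Risk difference, from Visit 6 |
|---|---|---|---|---|---|
| 0.01 | 4.3 | 1.44 | 1.91 | 7.2 points | 7.9 points |
| 0.02 | 8.2 | 1.38 | 1.84 | 11.5 points | 13.8 points |
| 0.05 | 18.1 | 1.25 | 1.64 | 14.7 points | 23.1 points |

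On the difference scale the rule is: observed excess = (1 − lead-in probability) × true excess, if the phases are independent. For a rarer class with a lead-in probability of 5% to 10% (assumed), a 20-point excess appears as 0.95 × 20 = 19 to 0.90 × 20 = 18 points.

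**Precision before Visit 6.** Comparator: 50 + 25 + 25 = 100 subjects on placebo without MCT. At an assumed 50% event rate, half-width = 1.96 × √(0.25 × (1/50 + 1/m)).

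- m = 50 (pooled placebo, already a default column): 1.96 × 0.5 × 0.200 = 19.6 points.
- m = 100: 1.96 × 0.5 × 0.173 = 17.0 points, 13% narrower.

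**Scope of that comparison.** It covers the extended arm's first four PQ Grass injections: 900 + 2700 + 6000 + 6000 = 15600 of 27600 SU, or 57%.

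**The case against.** The strongest defence is that the clock is right for the overall comparison. Counting from the first blinded injection gives all four arms the same start and planned time at risk and preserves randomisation. That stands. A reader might infer that the tables are biased against PQ Grass; they are not. The effect is dilution, and only the conventional arm's lead-in enters a PQ Grass column. The MCT-placebo lead-in stays in a placebo column.

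It can also be said that the lead-in is already visible. The by-injection table separates injections 1 to 4 from 5 to 10, the overview in SAP 5.8.2.3 gives event counts, which do not saturate, and listings carry study days. So a reader should not infer that the lead-in information is lost. Three gaps remain. The by-injection table covers only AEs, ADRs and severe AEs. Its per-injection counts cannot be added to give subjects with at least one event. And it does not pool the arms on identical placebo. Its time windows also leave 24 hours to 7 days unclear, and the event counts in the overview are not split by phase.

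A third point is that the Protocol assesses AEs within each group and plans no between-arm AE test or interval. That is true, so the precision gain bears on how the table is read and not on a formal analysis.

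Finally, the Safety Set rule, "Subjects will be analysed according to the treatment that they actually received", might be read as moving a conventional-arm subject who stops before Visit 6 into the placebo-without-MCT column. The documents do not support this. SAP 5.1.1 treats the two sets as identical when planned and actual treatment assignments agree, so actual treatment refers to the assigned sequence delivered and not to the products received before stopping.

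**Conclusion.** The point holds as a cheap improvement. The TEAE definition is workable and the overall tables should stay. What is missing is a phase-specific summary that separates about 9 weeks of placebo from PQ Grass exposure in the conventional arm and uses the randomised contrast of about 50 versus 100 before Visit 6.

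The lead-in length and arm sizes follow from the documents. The size of the dilution does not: it rests on assumed constant hazards of 0.01 to 0.05 per week, a doubling from Visit 6 and an 18-week window that the general TEAE definition does not impose. The precision figures assume a 50% event rate. It would be tempting to read heavy dilution into the SAE, AESI and SOC/PT tables too. The documents give no rates to support that, and where lead-in events of a class are rare the loss on the difference scale is small. The larger effect belongs to broad rows such as any TEAE.

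**What to change.** Keep the overall TEAE tables. In SAP 5.8.2.1 and 5.8.2.2 add two phases, defined by visit and identical for all arms, with each event assigned by its onset:

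- **Phase A:** from the Visit 2 injection to just before the Visit 6 injection. Compare the extended arm (about 50) with the three other arms pooled (about 100), all on placebo without MCT. State that this covers only the extended arm's first four PQ Grass injections, and how follow-up ends for subjects who never receive the Visit 6 injection.
- **Phase B:** from the Visit 6 injection to the last injection plus 28 days, among subjects who received the Visit 6 injection. Present it descriptively by arm. Label it as conditional on reaching Visit 6, a post-randomisation selection that may differ between arms, and as mixed placebo and active in the extended arm.

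At minimum, tabulate TEAEs, ADRs, SAEs, AESIs, local and systemic AEs and discontinuations by phase. The data are already collected and no study procedure changes. The cost is SAP wording and one further set of tables, plus the limited interpretability of Phase B.

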#### 5.8.2.2. Summary tables for analysis of adverse events

The number and percentage of subjects with

- TEAEs
- ADRs
- treatment emergent serious adverse events (SAEs)
- serious ADRs
- treatment emergent adverse events of special interest (AESIs)
- TEAEs leading to premature discontinuation of treatment
- ADRs leading to premature discontinuation of treatment
- TEAEs leading to temporary discontinuation of treatment
- ADRs leading to temporary discontinuation of treatment
- TEAEs leading to premature discontinuation of study
- ADRs leading to premature discontinuation of study
- local AEs
- systemic AEs

- other AEs, not classified as local or systemic AEs

will be summarised by treatment group, MedDRA SOC and PT.

For the analysis of the severity and the relationship of AEs, the worst severity and the strongest relationship per subject and type of AE will be used. The number and percentage of subjects with at least one AE by MedDRA SOC, PT and severity/relationship will be displayed only for

- all TEAEs
- all ADRs
- all serious adverse events (SAEs).

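### TEAEs are defined by onset after the first injection only, so an AE already present that worsens or becomes serious after dosing is left out of the treatment-emergent tables

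*SAP*

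**What the plan says.** SAP 5.8.2.1 divides AEs at the first injection. On one side: "Pre-Treatment adverse event: Any AE with date and time of onset prior to the first injection of study medication". On the other: "Treatment emergent AE (TEAE): Any AE with date and time of onset after first injection of study medication". SAP 5.8.2 repeats the division: "AEs will be reported separately as pre-treatment or screening period AEs (any AE occurring prior to the first injection of study medication", with everything after that injection called treatment emergent.

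The only departure from recorded onset is for incomplete data: "In case of (partially) missing date or time that could indicate a TEAE, it will be analysed as treatment emergent". The treatment-period subset also depends on onset: "TEAEs during the treatment period: Any AE with date and time of onset after first injection of study medication and up to and including date"; its window closes 28 days after the last injection.

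SAP 5.8.2.2 lists tables by SOC and PT that use this class, among them "treatment emergent serious adverse events (SAEs", "treatment emergent adverse events of special interest (AESIs" and "TEAEs leading to premature discontinuation of treatment". The ADR definition in 5.8.2.1 works differently: it depends on the relationship assessment (related, or assessment missing) and sets no condition on onset.

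**The concern.** A treatment-emergent table should show what appeared or got worse once treatment began. An onset rule captures only what appeared. An event that was mild before dosing and severe or serious after it keeps its pre-dose onset, and so keeps its pre-treatment label.

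The design makes such events possible. The protocol's schedule of activities collects AEs from Visit 1, performs skin prick testing and the conjunctival provocation test (CPT) at Visit 1, and repeats the CPT at Visit 2, where the first injection is also marked. In the extended arm that first injection is active; in the other three arms it is placebo without MCT (protocol, Overall design). A worsening after it could therefore bear on the comparison between arms.

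At stake is the completeness of the tables a reader would consult first for emergent harm. Within those tables this rule can only lower the counts.

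**Working it through.** The documents give no figure to reproduce. The check applies the rule to test events, traces the result through the planned outputs, and scales the effect of one subject.

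**1. The rule applied to five test events** (inputs: the definitions and missing-date rule in SAP 5.8.2.1)

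| Event | TEAE as written | TEAE with a worsening clause |
|---|---|---|
| Screening onset, resolves before dosing | No | No |
| Screening onset, worsens or becomes serious after dosing | No | Yes |
| CPT reaction timed before the first injection, worsens after it | No | Yes |
| Same CPT reaction, onset time missing | Yes | Yes |
| New onset after dosing | Yes | Yes |

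Two of the five change class. Rows three and four show a side effect: the same reaction is left out when its time is recorded and included when the time is missing.

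**2. Where the second event goes**

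- Left out, because the output is limited to TEAEs: in 5.8.2.2, the tables of TEAEs, treatment-emergent SAEs and AESIs, TEAEs leading to discontinuation (permanent or temporary) of treatment or to leaving the study, and TEAEs by severity and relationship; in 5.8.2.3, the local, systemic and other TEAE rows and the per-injection summary.
- Possibly still shown, because no such limit is stated: in 5.8.2.2, the ADR tables, the table of all SAEs by severity and relationship, and the SOC/PT tables of local, systemic and other AEs; in 5.8.2.3, the overview rows for any AE, severe AE, serious AE, AESI and AE leading to discontinuation; and the listings.

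The worst-severity rule in 5.8.2.2 does not bring the event back. It picks the severity to display, and the event has already been classed by onset.

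**3. Two tables compared for one subject**

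Take an AE with a recorded screening onset that worsens after an injection, is judged possibly related and ends treatment. The subject is counted among ADRs leading to premature discontinuation of treatment, because that definition ignores onset. The subject is not counted in the adjacent table, "TEAEs leading to premature discontinuation of treatment". A reader who expects related events to be a subset of TEAEs would find a related discontinuation with no matching TEAE.

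**4. Size per subject** (inputs: 150 subjects in ratio 2:2:1:1, protocol, Statistical methods)

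- Each PQ Grass arm: 150 × 2/6 = 50, so one subject is 100/50 = 2.0 percentage points.
- Pooled PQ Grass: 50 + 50 = 100, so 100/100 = 1.0 point.
- Each placebo arm: 150 × 1/6 = 25, so 100/25 = 4.0 points. This figure says nothing about worsening after PQ Grass.

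**The case against.** The strongest reply is that nothing need be lost. A reader might infer that a condition aggravated by PQ Grass disappears from the safety report. The documents do not support that: if the investigator judges it related, it is an ADR whatever its onset, and several overview rows and the listings carry no treatment-emergent limit as written. The protocol's safety endpoints are also worded in terms of AEs, not TEAEs. This stands, and it confines the point to the treatment-emergent outputs. It does not remove the point, because those outputs are planned and would be incomplete.

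A second reply is that the gap may be closed in data collection. If the eCRF enters a worsening as a new AE with its own onset, the present definition already captures it. The protocol supplied is a synopsis with no AE recording section, and some SAP pages before the table of contents were not available, so such a convention cannot be ruled out. SAP 5.8.2.1 does not mention one.

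Two other stronger readings also fail.

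- A reader might suppose that every CPT reaction on the first injection day is lost. It is lost only if it is recorded as an AE, timed before the injection, and then worsens. SAP 5.7.2.5.1 and 5.8.1 also name a Visit 2a, so the CPT and the first injection need not share a day for every subject.
- A reader might try to estimate the number affected. If 5 to 15% of subjects had an AE open at the first injection and 10 to 20% of those worsened, the count would run from 150 × 0.05 × 0.10 = 0.75 to 150 × 0.15 × 0.20 = 4.5. Neither rate has any anchor in the documents. The result also covers any worsening in all four arms, not SAEs, AESIs or discontinuations after PQ Grass.

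**Conclusion.** The point holds for the treatment-emergent outputs only. Followed as written, SAP 5.8.2 and 5.8.2.1 leave out of them an AE with a recorded pre-dose onset that worsens or becomes serious after the first injection. This is a stated rule with a one-directional effect, and it lets neighbouring tables in 5.8.2.2 disagree about the same subject.

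The number of subjects is unknown and probably small. Each one is worth 2 percentage points in a PQ Grass arm of about 50, which is noticeable mainly in sparse categories such as SAEs, AESIs and discontinuations. The conclusion assumes that no unseen convention already records a worsening as a new AE; if one exists, the gap largely closes and only the SAP wording needs attention. The change is worth making because safety is a stated objective and the correction is cheap.

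**What to change.** Use one mechanism only. Reclassifying the original record and also entering a separate worsening record would count one event twice, including in the event counts planned in 5.8.2.3.

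- **Either** extend the definition in 5.8.2.1, and match it in 5.8.2, to: *any AE with onset after the first injection, or any AE present before it that increases in severity or becomes serious after it*. Use the date of worsening as the reference date for the treatment-period subset and the per-injection summary.
- **Or** have each worsening entered as a new AE record with its own onset, state this in 5.8.2.1, and leave the original record as pre-treatment. If the eCRF instructions already require this, one sentence in the SAP is enough.

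The cost is one SAP sentence plus either a derivation or an eCRF completion note. The downside is that, before lock, data management must query AEs open at the first injection for a date of worsening, and a time where the per-injection summary needs it.
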